**The detailed contact information for reporting of SAEs is provided in the Investigator Study File.**

**For urgent safety issues**, please ensure all appropriate medical care is administered to the subject and contact the appropriate study team member listed in the Investigator Study File.

It is very important that the SAE report form be filled out as completely as possible at the time of the initial report. This includes the investigator's assessment of causality.

Any follow-up information received on SAEs should be forwarded within 1 business day of its receipt. If the follow-up information changes the investigator's assessment of causality, this should also be noted on the follow-up SAE form.

Preliminary SAE reports should be followed as soon as possible by detailed descriptions including copies of hospital case reports, autopsy reports, and other documents requested by the sponsor.

The investigator must notify his/her IRB/IEC of the occurrence of the SAE, in writing, if required by their institution. A copy of this communication must be forwarded to the sponsor to be filed in the sponsor's Trial Master File.

### 9.5.8.2 Reporting of Pregnancy and Exposure to Study Drug Through Breastfeeding

Any pregnancy in which the estimated date of conception is either before the last visit or within 28 days of last study treatment or any exposure to study drug through breastfeeding during study treatment or within 28 days of last study treatment must be reported.

If an adverse outcome of a pregnancy is suspected to be related to study drug exposure, this should be reported regardless of the length of time that has passed since the exposure to study treatment.

A congenital anomaly, death during perinatal period, an induced abortion, or a spontaneous abortion are considered to be an SAE and should be reported in the same time frame and in the same format as all other SAEs ([Section 9.5.8.1](#)).

Pregnancies or exposure to study drug through breastfeeding must be reported by fax or email as soon as possible but no later than 1 business day from the date the investigator becomes aware of the pregnancy. The contact information for the reporting of pregnancies and exposure to study drug through breastfeeding is provided in the Investigator Study File. The Pregnancy Report Form must be used for reporting. All pregnancies must be followed to outcome. The outcome of the pregnancy must be reported as soon as possible but no later than 1 business day from the date the investigator becomes aware of the outcome.

A subject who becomes pregnant must be withdrawn from the study. A subject who becomes pregnant may remain in the study if the investigator judges that the potential benefit to the subject outweighs any potential risk to the subject or the fetus and the subject gives informed consent for the further participation.

### 9.5.8.3 Reporting of Events Association with Special Situations

#### 9.5.8.3.1 REPORTING OF ADVERSE EVENTS ASSOCIATED WITH STUDY DRUG OVERDOSE, MISUSE, ABUSE, OR MEDICATION ERROR

Adverse events associated with study drug overdose, misuse, abuse, and medication error refer to AEs associated with uses of the study drug outside of that specified by the protocol. Overdose, misuse, abuse, and medication error are defined as follows:

Overdose	Accidental or intentional use of the study drug in an amount higher than the protocol-defined dose
Misuse	Intentional and inappropriate use of study drug not in accordance with the protocol
Abuse	Sporadic or persistent intentional excessive use of study drug accompanied by harmful physical or psychological effects
Medication error	Any unintentional event that causes or leads to inappropriate study drug use or subject harm while the study drug is in the control of site personnel or the subject

All AEs associated with overdose, misuse, abuse, or medication error should be captured on the Adverse Event CRF and also reported using the procedures detailed in [Section 9.5.8.1](#) even if the AEs do not meet serious criteria. Abuse is always to be captured as an AE. If the AE associated with an overdose, misuse, abuse, or medication error does not meet serious criteria, it must still be reported using the SAE form and in an expedited manner but should be noted as nonserious on the SAE form and the Adverse Event CRF.

#### 9.5.8.4 Expedited Reporting

The sponsor must inform investigators (or, as regionally required, the head of the medical institution) and regulatory authorities of reportable events, in compliance with applicable regulatory requirements, on an expedited basis (ie, within specific time frames). For this reason, it is imperative that sites provide complete SAE information in the manner described above.

#### 9.5.8.5 Breaking the Blind

Not applicable.

#### 9.5.8.6 Regulatory Reporting of Adverse Events

Adverse events will be reported by the sponsor or a third party acting on behalf of the sponsor to regulatory authorities in compliance with local and regional law and established guidance. The format of these reports will be dictated by the local and regional requirements.

All studies that are conducted within any European country will comply with European Good Clinical Practice Directive 2005/28/EC and Clinical Trial Directive 2001/20/EC. All suspected unexpected serious adverse reactions (SUSARs) will be reported, as required, to the competent authorities of all involved European member states.

### 9.5.9 Completion/Discontinuation of Subjects

The investigator may withdraw the subject from the study at any time for safety or administrative reasons. A subject may elect to discontinue the study at any time for any reason. All subjects who discontinue the study are to complete the study's early discontinuation procedures indicated in the Schedule of Procedures/Assessments ([Table 6](#)).

The investigator will promptly explain to the subject involved that the study will be discontinued for that subject and provide appropriate medical treatment and other necessary measures for the subject. A subject who has ceased to return for visits will be followed up by mail, phone, or other means to gather information such as the reason for failure to return, the status of treatment compliance, the presence or absence of AEs, and clinical courses of signs and symptoms.

Subjects who discontinue early from the study will be discontinued for 1 of these primary reasons: AE(s), lost to follow-up, subject choice, withdrawal of consent, pregnancy, study terminated by sponsor, or other. In addition to the primary reason, the subject may indicate 1 or more of secondary reasons for discontinuation. Study disposition information will be collected on the Subject Disposition CRF.

### 9.5.10 Confirmation of Medical Care by Another Physician

The investigator will instruct subjects to inform site personnel when they are planning to receive medical care by another physician. At each visit, the investigator will ask the subject whether he/she has received medical care by another physician since the last visit or is planning to do so in the future. When the subject is going to receive medical care by another physician, the investigator, with the consent of the subject, will inform the other physician that the subject is participating in the clinical study.

## 9.6 Data Quality Assurance

This study will be organized, performed, and reported in compliance with the protocol, SOPs, working practice documents, and applicable regulations and guidelines. Site audits will be made periodically by the sponsor's or the CRO's qualified compliance auditing team, which is an independent function from the study team responsible for conduct of the study.

### 9.6.1 Data Collection

Data required by the protocol will be collected on the CRFs and entered into a validated data management system that is compliant with all regulatory requirements. As defined by ICH guidelines, the CRF is a printed, optical, or electronic document designed to record all of the protocol-required information to be reported to the sponsor on each study subject.

Data collection on the CRF must follow the instructions described in the CRF Completion Guidelines. The investigator has ultimate responsibility for the collection and reporting of all clinical data entered on the CRF. The investigator or designee as identified on Form FDA 1572 must sign the completed CRF to attest to its accuracy, authenticity, and completeness.

Completed, original CRFs are the sole property of Eisai and should not be made available in any form to third parties without written permission from Eisai, except for authorized representatives of Eisai or appropriate regulatory authorities.

### 9.6.2 Clinical Data Management

All software applications used in the collection of data will be properly validated following standard computer system validation that is compliant with all regulatory requirements. All data, both CRF and external data (eg, laboratory data), will be entered into a clinical system.

## 9.7 Statistical Methods

All statistical analyses will be performed by the sponsor or designee after the study is completed and the database is locked and released. Statistical analyses will be performed using WinNonlin and SAS software or other validated statistical software as required. Details of the statistical analyses will be included in a separate statistical analysis plan (SAP).

Descriptive statistics will be used for continuous variables using n, mean, standard deviation (SD), median, Q1 (25th percentile), Q3 (75th percentile), minimum, and maximum, unless otherwise specified. Categorical variables will be summarized as number (percent) of subjects.

### 9.7.1 Statistical and Analytical Plans

For purposes of the final analysis, data cutoff will occur when the last enrolled subject completes 6 cycles of treatment (ie all subjects have been followed by a minimum of 6 cycles) or subjects discontinue early, whichever occurs first. The statistical analyses of study data are described in this section. Further details of the analytical plan will be provided in the SAP, which will be finalized before database lock.

#### 9.7.1.1 Study Endpoints

##### **Primary Endpoints (Dose Escalation part):**

- Safety/tolerability profile of E7046.
- MTD and/or the RP2D.

##### **Secondary Efficacy endpoints:**

- Objective response rate

The ORR is the proportion of subjects achieving a best overall response of confirmed partial or complete response (irPR + irCR), according to irRECIST ([Appendix 1](#)) from first dose date until disease progression/recurrence. Subjects who do not have a tumor response assessment for any reason will be considered nonresponders and will be included in the denominator when calculating the response rate.

- Duration of response

Duration of response is defined as the time from the date of first documented confirmed irCR/irPR until the first documentation of confirmed disease progression or death, whichever comes first.

- Progression-free survival

Progressive-free survival is defined as the time from first dose date to the date of the first documentation of confirmed disease progression or death (whichever occurs first) using irRECIST. The censoring rule for events will be defined in the SAP.

- Disease control rate

The DCR is the proportion of subjects achieving irPR + irCR + irSD from first dose date until disease progression/recurrence.

- Clinical benefit rate

The CBR is the proportion of subjects achieving irPR + irCR + irSD [lasting at least 24 weeks] from first dose date until disease progression/recurrence.

### **Exploratory endpoints:**

- ORR, DCR, CBR, PFS according to modified RECIST 1.1
- Effect of E7046 on tumor  $^{18}\text{FDG}$  uptake and volume will be explored as potential early response biomarkers. Variables will include total tumor volume of target lesions, metabolic tumor volume (SUV  $>2.5$ ), maximum SUV of a single pixel, metabolic peak of a 1 cm spot, and summed SUVs of target lesions. Summary statistics and change from baseline will be presented.
- Effect of E7046 on  $^{18}\text{FDG}$  uptake by spleen and/or draining lymph nodes will be explored as a potential biomarker of immune activation. Variables will include total volume and metabolic volume of spleen and, where possible, draining lymph nodes. Summary statistics and change from baseline will be presented.

#### 9.7.1.2 Definitions of Analysis Sets

**Full Analysis Set** will include all subjects who received at least one dose of study drug. This will be the primary analysis set for efficacy evaluations, as well as for demographic and baseline characteristics. This analysis set will also constitute the **Safety Analysis Set**.

**DLT Evaluatable Set** will consist of those subjects who are evaluable for the DLTs ([Section 9.1.1.2](#)). This will be the analysis set for DLT analysis.

**Pharmacokinetic (PK) Analysis Set** will include all subjects who have received at least one dose of study drug and have at least one evaluable plasma concentration.

#### 9.7.1.3 Subject Disposition

The number (percentage) of randomized and treated subjects will be summarized as well as subjects who completed the study/discontinued from the study and reasons for discontinuation by treatment group. The number (percentage) of subjects who completed the study treatment/discontinued from the study treatment and reasons for discontinuation will also be summarized by treatment cohort.

#### 9.7.1.4 Demographic and Other Baseline Characteristics

Demographic and other baseline characteristics for the Full Analysis Set will be summarized and listed for each treatment cohort. For continuous demographic/baseline variables including age, weight, and vital signs, results will be summarized and presented as N, mean, standard deviation, median, Q1, Q3, minimum and maximum values. For categorical variables such as race/ethnicity, the number and percentage of subjects will be used.

#### 9.7.1.5 Prior and Concomitant Therapy

All investigator terms (verbatim terms) for medications recorded in the CRF will be coded to an 11-digit code using the World Health Organization Drug Dictionary (WHO DD) drug codes. Prior medications will be defined as medications that stopped before the first dose of study drug. Concomitant medications will be defined as medications that (1) started before the first dose of study drug and were continuing at the time of the first dose of study drug, or (2) started on or after the date of the first dose of study drug up to 30 days after the subject's last dose. A listing of prior and concomitant medications will be included in the clinical study report for this protocol.

#### 9.7.1.6 Dose Escalation Primary Endpoints Analyses

**Safety/tolerability profile** of E7046 will be assessed. The incidence of treatment-emergent adverse events (TEAEs) and SAEs together with all other safety parameters will be summarized, by dose levels.

**Maximum tolerated dose.** The incidence of DLTs by dose level will be tabulated. The MTD will be determined per protocol definition.

**RP2D.** The RP2D will be selected as described in [Section 9.1.1.4](#).

### 9.7.1.7 Efficacy Analyses

The ORR, response duration, time to response, PFS, DCR, and CBR will be listed and descriptively summarized as appropriate.

- Response duration and time to response: Summary statistics (median Q1, Q3, and range) for will be summarized on subjects achieving a best overall response of confirmed partial or complete response (irPR + irCR). The time to response will be censored at the last tumor assessment for subjects who leave the study before a response, death or progression is observed.
- PFS: Subjects who discontinue from the study for reasons other than progression of disease will be treated as right-censored observations at the time of the last response evaluation (subjects who withdraw from the study due to progressive disease will be considered to have a disease progression between the last visit and the time of withdrawal). PFS (by irRECIST) will be reported in both summary tables and Kaplan–Meier curve.

### 9.7.1.8 Pharmacokinetic Analyses

Plasma and urine concentrations of E7046 and its major metabolite M1 will be tabulated and summarized by dose level, day, and time. PK parameters will be derived from plasma concentrations by noncompartmental analysis using actual times. Minimally, the following PK parameters will be calculated: maximum drug concentration ( $C_{max}$ ), time to reach maximum concentration following drug administration ( $t_{max}$ ), area under the concentration  $\times$  time curve (AUC); and if data permit, elimination half-life ( $t^{1/2}$ ), total body clearance (CL), volume of distribution (Vd), renal clearance (CLr), accumulation ratio (R), and fraction excreted (fe).

### 9.7.1.9 Pharmacodynamic, Pharmacogenomic, and Other Biomarker Analyses

Pharmacodynamic, PG and other biomarker analyses may be performed and reported separately. Details of these analyses will be described in a separate analysis plan.

### 9.7.1.10 Safety Analyses

Evaluation of safety will be performed on the Safety Analysis Set. Safety data to be evaluated include AEs, clinical laboratory results, vital signs, ECGs, and the results of physical examinations.

Safety assessments will consist of monitoring and recording all AEs and SAEs, using CTCAE version 4.03; regular laboratory evaluation for hematology, blood chemistry, and urine values; and regular performance of physical examinations, periodic measurement of vital signs, ECGs, and MUGA scans at baseline and as clinically indicated.

Safety parameters will be summarized using descriptive statistics (mean, standard deviation, median, Q1, Q3, and range for continuous variables; numbers and percentages for categorical measures).

The effects of E7046 on cardiovascular repolarization will be evaluated via 12-hour, 12-lead continuous Holter/ECG monitoring during Cycle 1 Day 1 and Day 8 in the Dose Escalation part of the study only. Individual ECGs will be extracted in replicate from the Holter recordings at specified time points and will be evaluated by a central laboratory. QT intervals will be measured from Lead II and will be corrected for QTc using Fridericia's (QTcF) correction factors. The primary QTc parameter will be QTcF. Secondary parameters (heart rate, PR and QRS) and T wave morphology will be evaluated. Potential effects of E7046 will be evaluated as change-from predose baseline heart rate, PR, QRS and QTcF by post-dosing timepoint. For purposes of QT assessment, exposure response analysis will be performed of the relationship between E7046 plasma levels and  $\Delta$ QTcF.

Safety ECGs will be analyzed using descriptive statistics for ECG parameters and changes from baseline will be presented by treatment cohort abnormal readings will be identified as those outside (above or below) the reference range. ECG findings will be summarized.

#### 9.7.1.10.1 EXTENT OF EXPOSURE

The number of cycles/days on treatment, quantity of study drug administered, and the number of subjects requiring dose reductions, treatment interruption, and treatment discontinuation due to AEs will be summarized.

#### 9.7.1.10.2 ADVERSE EVENTS

The AE verbatim descriptions (investigator terms from the CRF) will be classified into standardized medical terminology using the Medical Dictionary for Regulatory Activities (MedDRA). Adverse events will be coded to the MedDRA (Version 18.0 or higher) lower level term (LLT) closest to the verbatim term. Adverse events will be presented by MedDRA preferred term (PT) nested within primary system organ class (SOC).

A TEAE is defined as an AE that emerges during treatment, having been absent at pretreatment (Baseline), or

- Reemerges during treatment, having been present at pretreatment (Baseline) but stopped before treatment, or
- Worsens in severity during treatment relative to the pretreatment state, when the AE is continuous.

Only those AEs that were treatment emergent will be included in summary tables. All AEs, treatment-emergent or otherwise, will be presented in subject data listings.

The TEAEs will be summarized by treatment cohort. The incidence of TEAEs will be reported as the number (percentage) of subjects with TEAEs by SOC and PT. A subject will be counted only once within a SOC and PT, even if the subject experienced more than 1 TEAE within a specific SOC and PT. The number (percentage) of subjects with TEAEs will also be summarized by maximum severity (mild, moderate, or severe) and by relationship to study drug (Yes [related] and No [not related]), respectively.

#### 9.7.1.10.3 LABORATORY VALUES

Laboratory results will be summarized using Système International (SI) units, as appropriate. For all quantitative parameters listed in [Section 9.5.5.3](#), the actual value and the change from baseline to each postbaseline visit and to the end of will be summarized by visit and treatment cohort using descriptive statistics. Qualitative parameters listed in [Section 9.5.5.3](#) and change from baseline values will be summarized using frequencies (number and percentage of subjects).

#### 9.7.1.10.4 VITAL SIGNS

Descriptive statistics for vital signs parameters (ie, diastolic and systolic BP, pulse, respiratory rate, temperature, weight and changes from baseline will be presented by day and time after dosing and treatment cohort.

**MUGA Scans:** MUGA scans and/or echocardiograms will be assessed locally to determine LVEF. Summary statistics (standard deviation, median, and range) for LVEF changes from baseline will be calculated and summarized.

### 9.7.2 Determination of Sample Size

The sample size of 30 to 40 subjects is considered adequate for the purposes of selecting a dose.

The expected sample size for the dose escalation part of this trial will be up to 24 subjects. Per the dose escalation design adopted and modified from the traditional 3+3 design ([Section 9.1.1.1](#)), there will be a maximum of 4 planned cohorts and there will be 6 subjects each cohort to allow for adequate assessment of tolerability, clinical benefit, PK, PD data and integrated evaluation of safety so as to select RP2D. Additional 6 to 16 subjects will be enrolled in the expansion cohort to confirm RP2D.

The dose escalation part and the extension part yield a total maximum sample size of 40 subjects.

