## **Study Population**

This study will be conducted in subjects with tumor types that harbor high levels of myeloid infiltrate based on the Cancer Genome Atlas (TCGA), in keeping with the expected action of E7046 on intratumoral immunosuppressive cells of myeloid lineage.

Approximately 30 to 40 subjects will be enrolled, 24 in the dose escalation part, and 6 to 16 subjects in the cohort expansion.

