### 9.1.1 Dose Escalation

#### 9.1.1.1 Dose Escalation Design

E7046 will be tested in sequential escalating dose cohorts of 6 subjects per cohort, at the dose levels shown in [Table 1](#). Subjects will be assigned to a dose level in the order of study entry. Intermediate dose levels may be explored.

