- If  $\leq 1$  of 6 subjects in a dose cohort experiences a DLT, then 6 subjects will be enrolled at the next higher dose level. Dose escalation will continue until a dose level is reached where  $\geq 2$  subjects experience a DLT, or when 750 mg is reached based on

an integrated evaluation of safety, tolerability, clinical benefit, PK, and pharmacodynamic data, for all dose levels tested.

[figure not shown]
Additional enrollment (if necessary)

If needed for selection of RP2D, an additional 3 subjects may be enrolled at 1 or 2 selected dose levels.

Panel A: Overall Dose Escalation Schema

Panel B: First Dose Cohort (Staggered dosing)

ssIR = suspected severe immune reaction

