Subjects who for reasons other than drug related toxicity or a DLT, fail to complete 75% of the planned total dose in Cycle 1, (equivalent to 16 out of 21 days) will be replaced.

Assessment of DLTs will be discussed and agreed to by investigator(s) and sponsor physician prior to proceeding to the next dose level, and the decision will be documented.

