### 9.1.2 Cohort Expansion

An expansion cohort of 6 to 16 subjects will be enrolled and treated at the RP2D after completion of the dose escalation part. The objective is to further evaluate safety and efficacy of E7046 at the RP2D and further characterize PK and PD. Subjects will be selected from the same tumor types as in the dose escalation part.

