13.3 Dose-Limiting Toxicities

Dose-limiting toxicities (DLTs) are any of the following drug related toxicities (any toxicities considered related, probably related, or possibly related to E7046) occurring during Cycle 1 as judged by the investigator.

- Nonhematologic toxicity \geq Grade 3 (except diarrhea, nausea and vomiting unless lasting >3 days despite optimal supportive care)
- Hematologic toxicity:
 - Grade 4 neutropenia for ≥ 5 days, or Grade 3 neutropenia with fever (fever is 38.4 °C),
 - Grade 4 thrombocytopenia, or Grade 3 thrombocytopenia with bleeding or lasting >7 days
- Any other toxicity assessed as related to E7046 treatment, and which in the opinion of a study investigator(s) the sponsor physician constitutes a dose-limiting toxicity
- Subjects who have missed > 4 days of dosing in Cycle 1 due to drug-related toxicity (but not qualifying for a DLT) will be assessed as experiencing a DLT.

Grading of toxicities is based on National Cancer Institute - Common Terminology Criteria for Adverse Events (NCI CTCAE) v4.03 (Section 13.4).

Adverse events occurring after Cycle 1 may be considered DLTs upon discussion between the investigator and the sponsor physician.

The following toxicities will not be considered DLTs:

- Grade 3 adverse event of tumor flare (defined as local pain, irritation, or rash localized at sites of known or suspected tumor)
- Grade 3 immune-related adverse event (irAE) that resolves to \leq Grade 1 within 7 days
 - An irAE, a subset of AEs, is defined as a clinically significant adverse event of any organ that is associated with study drug exposure, of unknown etiology, and is consistent with an immune-mediated mechanism. Serologic, immunologic, and

histologic (biopsy) data should be used to support an irAE diagnosis. Appropriate efforts should be made to rule out neoplastic, infectious, metabolic, toxin, or other etiologic causes of the irAE.

Subjects who do not complete at least 17 of 21 days of dosing in Cycle 1 due to reasons other than treatment related toxicity will be replaced for the purpose of DLT evaluation.

Assessment of DLTs will be discussed and agreed to by investigator(s) and sponsor physician prior to proceeding to the next dose level, and the decision will be documented.

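### Does calling 40 the maximum sample size need correcting, when the protocol's own options can take enrolment past it?

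*Protocol*

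**What the plan says.** Protocol 9.7.2 expects up to 24 subjects in dose escalation, because "there will be a maximum of 4 planned cohorts" with 6 subjects in each, and adds 6 to 16 in the expansion. It concludes that "The dose escalation part and the extension part yield a total maximum sample size of 40 subjects". SAP 4 repeats that sentence, having opened by describing the sample size as approximately 40.

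The protocol synopsis (Study Population) says: "Approximately 30 to 40 subjects will be enrolled, 24 in the dose escalation part, and 6 to 16 subjects in the cohort expansion". Protocol 9.3 says much the same.

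Four other provisions bear on the total:

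- **Extra subjects** (Protocol 9.1.1.1, additional enrolment): "If needed for selection of RP2D, an additional 3 subjects may be enrolled at 1 or 2 selected dose levels".
- **Intermediate levels** (Protocol 9.1.1.1): "Intermediate dose levels may be explored".
- **Replacement** (Protocol 9.1.1.2): subjects who fall short of 75% of the planned Cycle 1 dose for reasons other than drug toxicity or a DLT ("equivalent to 16 out of 21 days) will be replaced"). SAP 13.3 has a similar rule, under which such subjects "will be replaced for the purpose of DLT evaluation". The two documents set the threshold one day apart; that is a separate matter and does not affect the sums here.
- **Expansion** (Protocol 9.1.2): "An expansion cohort of 6 to 16 subjects will be enrolled and treated at the RP2D after completion of the dose escalation part". Section 9.1.1.4 also lets expansion take place at up to two dose levels, with up to 6 additional subjects each, if candidate doses cannot be told apart.

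**The concern.** A number called a maximum should hold when every permitted option is used, and this one does not. It counts the planned cohorts and the full expansion and nothing else. Replacement is mandatory and uncapped, the extra-subject option and the intermediate levels are uncounted, and no section says that the expansion shrinks to keep the total at 40.

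Two readings are then possible. If 40 is the planned number, the study can properly enrol more than the maximum both documents state. If 40 is a binding limit, extra and replacement subjects take places from the expansion, and neither document says so. At stake would be the size of the expansion cohort, which is meant to characterise safety, efficacy, PK and PD at the recommended dose, and the enrolment figure that sites and ethics committees see.

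**Working it through.** **Inputs.** Planned cohorts: 4, with 6 subjects each (Protocol 9.7.2). Expansion: 6 to 16 (Protocol 9.1.2 and 9.7.2). Extra subjects: 3 in all, or 3 at each of two levels (Protocol 9.1.1.1; the visible text supports either reading, and the escalation figure is not available). Replacement: one more enrolled subject per subject replaced, with no cap.

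**The plan's own figure.** Lower end 4 × 6 + 6 = 30. Upper end 4 × 6 + 16 = 40. Both match the documents, so there is no addition error.

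**How enrolment can pass 40**, with all four planned cohorts filled and an expansion of 16:

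| Provision used | Sum | Total enrolled |
|---|---|---|
| One replacement | 24 + 1 + 16 | 41 |
| 3 extra subjects in all | 24 + 3 + 16 | 43 (3/40 = 7.5% over) |
| 3 extra at each of two levels | 24 + 6 + 16 | 46 (6/40 = 15% over) |
| One intermediate cohort, assumed to hold 6 | 24 + 6 + 16 | 46 |

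The documents give no rate of subjects not evaluable for DLT. Assuming 5%, 10%, 15% or 20%, the number needed for 24 evaluable subjects is 24/(1 − rate), rounded up: 26, 27, 29 or 30. Adding 16 gives 42, 43, 45 or 46 enrolled.

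**How the same provisions can stay within 40:**

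- 3 extra subjects and an expansion of 13: 24 + 3 + 13 = 40.
- 6 extra subjects and an expansion of 10: 24 + 6 + 10 = 40. With the minimum expansion the total is 24 + 6 + 6 = 36.
- Three planned cohorts with the extra-subject option and full expansion: 18 + 3 + 16 = 37, or 18 + 6 + 16 = 40.
- Three planned cohorts and one intermediate cohort (again assumed to hold 6): 18 + 6 + 16 = 40.
- Expansion at two dose levels: 2 × 6 = 12, which fits inside 6 to 16 if counted there.

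These sums are before replacements. Dose Level -1 does not drive the total up, because it opens only when Dose Level 1 is stopped: 6 + 6 = 12 subjects at most at that stage, before replacements.

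**What uses the number 40.** Escalation and the maximum tolerated dose depend on DLT counts within a cohort of 6 (Protocol 9.1.1.1 and 9.1.1.3). The recommended dose comes from an integrated judgement (9.1.1.4). The Full and Safety Analysis Sets take everyone dosed, and the DLT set takes everyone evaluable (Protocol 9.7.1.2, SAP 5.2.1). Analyses are descriptive, with Kaplan-Meier estimates for the time-to-event endpoints. Neither sample-size section gives a power, an error rate or a target precision. None of these would be computed differently at 41, 43 or 46.

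**The case for a change.** The strongest case for acting is that the sentence in 9.7.2 carries no qualifier. The word planned attaches to the cohorts, not to the concluding total, and SAP 4 calls the same number approximate and a maximum within one section. Replacement is not optional. Reading 40 as a count of evaluable places would excuse replacements, but the sample-size sections do not say this, and a replaced subject who was dosed stays in the Full and Safety Analysis Sets. Nor would that reading cover the extra subjects, who are new places. Correcting the label would cost a few words.

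The literal point stands: 40 is not a ceiling that the protocol's rules deliver. What does not stand is the claim that a reader is left stranded. The sentence closes a paragraph that has just set out the two parts, calling the escalation size expected and the cohorts planned, so the natural reading is the top of that sum. A total described as approximate in the synopsis, Protocol 9.3 and SAP 4 is hard to read as binding, and no section describes enforcing it.

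If it were enforced, the extra-subject option would leave 40 − 27 = 13 or 40 − 30 = 10 expansion places before replacements, both inside the stated range. Falling below the minimum of 6 would need 35 enrolled in escalation: 8 replacements on top of 27, or 5 on top of 30, under a limit the documents do not state. Writing such a limit in would be a new enrolment rule, not a clarification.

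**Conclusion.** The observation is accurate but calls for no change. Forty is the top of the planned range, 4 × 6 + 16, and the word maximum is loose. With all planned places filled, the extra-subject option takes enrolment to 43 or 46, and replacements or intermediate levels can add to that. With a smaller expansion, or fewer cohorts opened, the total can stay at or below 40.

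There is nothing to gain for the trial's results. No decision rule, analysis set, estimate or stated precision depends on 40, and the conclusions would be equally sound under either reading. The study team can read the figure as the planned upper end, and the report will give the number actually treated and evaluable.

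The figures assume that all four planned cohorts are filled where stated. An intermediate cohort of 6 and a non-evaluable rate of 5% to 20% are assumptions the documents do not supply; the conclusion does not depend on them.
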